## 12 Adverse Events and Device Deficiencies

### 12.1 Adverse Events

All AEs, including non-subject AEs, will be collected throughout a subject's participation, starting from the time the informed consent form is signed, through 30 days after the day of the procedure, regardless of their severity, relationship to the Hugo™ RAS system or study procedures.

After 30 days, all AEs will be assessed by the surgeon and those AEs deemed attributable to the procedure and / or study device will be reported. All deaths will be collected throughout a subject's participation, regardless of relatedness.

Reporting of these events to Medtronic will occur on an AE Form, including event description, date of AE, treatment, resolution, assessment of both the seriousness of the AE and the relatedness to the study device, procedure. Each AE must be recorded on a separate AE eCRF.

AE definitions used in this study (**Table 8**) are based on ISO 14155:2020 (Clinical Investigation of Medical Devices for Human Subjects – Good Clinical Practice). Documented pre-existing conditions are not considered AEs unless the nature or severity of the condition has worsened. See **Section 14** for details regarding AE analyses in each study analysis set. In addition, AEs impacting users or other persons (non-subject AEs) will be collected on a non-subject AE CRF.

Any unresolved procedural or device-related events that are still ongoing past study exit will be monitored by the Investigator per their institutional standard-of-care.

Unavoidable adverse events (UAE) (those that are inherent to the procedure and are expected to occur in all subjects for an expected duration) listed in **Table 11** will not be captured or reported unless the adverse event worsens or persists outside the stated timeframe post procedure. **Section 11.1** includes a list of several but not all-encompassing anticipated adverse events.

All Serious Adverse Events (SAE), deaths, and Surgical Site Events (SSEs) will be adjudicated by an independent CEC through 30 days post-procedure as of revision 5.0 of the protocol.

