## 12.4 Definitions/Classifications

This study is not within the scope of ISO 14155:2020 but will use AE definitions according to ISO 14155:2020 for consistency in reporting.

This study will collect the following:

- All adverse events, including non-subject AEs, from the time the informed consent is signed through the first 30 days after the day of the procedure, regardless of their severity, relationship to the Hugo™ RAS system or study procedures. After 30 days, all AEs will be assessed by the surgeon and those AEs deemed attributable to the procedure and/or study device will be reported. All deaths will be collected throughout a subject's participation, regardless of relatedness.
- All device deficiencies (all components of the Hugo™ RAS system)

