To establish the relatedness, not all the criteria listed above might be met at the same time, depending on the type of device/procedures and the event. For purposes of analysis categories considered “related” will include Possible, Probably, and Causal.

*Medtronic Business Restricted*

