## 14.5 Secondary Objective(s)

The secondary objective of this study is to demonstrate the Medtronic Hugo™ RAS system performs as intended when used in inguinal and ventral hernia repair. The secondary endpoints of this study will assess the overall performance of the Medtronic Hugo™ RAS system when used for the robotic surgery.

The following short-term secondary endpoints will be assessed through 30 days in all treated subjects:

- Complication rate: Overall rate of subjects with one or more procedure- and/or device-related complications (Clavien-Dindo Grade I or higher), from the first incision through 30 days post-procedure
- Major complication rate: Overall rate of subjects with one or more major procedure- and/or device-related complications (Clavien-Dindo Grade III or higher), from the first incision through

*Medtronic Business Restricted*

30-days post-procedure

- Operative time
- Readmission rate (through 30 days post-procedure): the proportion of subjects with any hospital readmissions through 30-days post-procedure
- Reoperation rate (through 30 days post-procedure): the proportion of subjects with any reoperation on the same target hernia through 30-days post-procedure
- Recurrence rate (through 30 days post-procedure): the proportion of subjects with any recurrences of hernia on the same anatomical region as the target hernia through 30-days post-procedure

The following long-term secondary endpoints will be assessed through 2 years in all treated subjects:

- Recurrence rate (through 2 years post-procedure): the proportion of subjects with any recurrences of hernia on the same anatomical region as the target lesion through 2 years post-procedure

The analysis set for the secondary objectives will be the FAS with available data. The secondary endpoints will be analyzed for the inguinal and ventral hernia cohort respectively.

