7.9.3.1 Objectives, Endpoint Definitions and Derivations

Endpoint	Endpoint Definition and Derivation
Any complication rate through 30 days post procedure	Overall rate of subjects with one or more procedure- and/or device-related complications (Clavien-Dindo Grade I or higher), from the first incision through 30 days post-procedure. CD Grade and device and/or procedure relatedness is assessed by the study site. Where CEC assessment of device and/or procedure relatedness is available, it will be used as the primary source of relatedness.
Major complication rate through 30 days post procedure	Overall rate of subjects with one or more major procedure- and/or device-related complications (Clavien-Dindo Grade III or higher), from the first incision through 30-days post-procedure. CD Grade and device and/or procedure relatedness is assessed by the study site. Where CEC assessment of device and/or procedure relatedness is available, it will be used as the primary source of relatedness.
Operative time	Time from skin incision to skin closure. This will also be summarized separately for the following: 
 • Unilateral operative time for inguinal hernia • Bilateral operative time for inguinal hernia • Operative time for ventral hernia
Readmission rate through 30 days post procedure	Admission for a direct consequence or complication associated with the treated hernia or with the surgical procedure to treat the hernia. A readmission is determined by the study site on the AE CRF.
Reoperation rate through 30 days post procedure	Operation for a direct consequence or complication associated with the treated hernia or with the surgical procedure to treat the hernia. A reoperation is determined by the study site on the AE CRF.
Recurrence rate through 30 days post procedure	Clinical hernia recurrence is defined as a palpable fascial defect and/or a clinically manifested bulge within 7 cm of the original repair, exacerbated by a Valsalva maneuver during physical examination by a study investigator. A recurrence is determined by the study site on the AE CRF. Only confirmed recurrence will be included in this rate. Secondary hernias will be differentiated from primary hernia recurrences by the study investigator. Secondary hernias are defined as a hernia located >7 cm of the original hernia repair. Secondary hernias will be excluded from hernia recurrence reporting for all hernia recurrence endpoints.

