Recurrence rate through 2 years post procedure	This analysis uses similar definitions as recurrence rate through 30 days. Note: Suspected hernia recurrence(s) reported by a subject, but not confirmed by an investigator, will not be considered as a clinical hernia recurrence for this endpoint, but will be reported separately as a subject-reported recurrence in the final report.

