7.9.3.5 Determination of Subjects/Data for Analysis

The analysis set for the secondary objectives will be the FAS with available data. Data availability for assessments through 30 days will follow the logic described in section 7.4. The secondary endpoints will be analyzed for the inguinal and ventral hernia cohorts separately and when combined.

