7.10 Safety Evaluation

Additional summaries of safety will be assessed for the FAS population. These include summaries of adverse events and device deficiencies (DD). AEs and DDs will be summarized with number of events, number of subjects who experienced the event, and percentage of subjects who experienced one or more events.

AEs for all subjects will be collected from consent through the study exit. AEs and DDs will be coded and summarized using the most recent version of Medical Dictionary for Regulatory Affairs (MedDRA). Serious Adverse Events (SAE), deaths, and Surgical Site Events (SSEs) will be adjudicated by an independent CEC as defined in the CIP. Cases where the investigator's classification does not match CEC's adjudication classification, both determinations will be provided within the final report; however, the CEC's adjudication will be used for data analysis.

AEs occurring in subjects excluded from the FAS will be followed post-consent through study exit and will be reported in the CSR. These AEs will not be included in the FAS summary analysis for either AE reporting or the analysis of the primary and secondary endpoints.

For the FAS, AEs will be reported by the type (preferred term), seriousness, and procedure/device relatedness. Summaries will focus on the time periods which are complete as of the snapshot for the report, with special attention to those periods which start during the procedure (e.g. during the procedure to 30 days after the procedure).

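### Two-year recurrence is taken from an AE form that the protocol filters by attribution after day 30, and its 2-year denominator is not defined

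*SAP*

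**What the plan says.** **Source of the endpoint.** SAP 7.9.3.1 states for recurrence: "A recurrence is determined by the study site on the AE CRF". Its row for the 2-year endpoint adds: "This analysis uses similar definitions as recurrence rate through 30 days".

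**What reaches the AE form after day 30.** Under protocol 12.1 the surgeon assesses later AEs and "those AEs deemed attributable to the procedure and / or study device will be reported". Protocol 12.4 repeats the rule: "those AEs deemed attributable to the procedure and/or study device will be reported". Deaths are the only exemption from this filter.

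**What the endpoint is.** Protocol 5.2.2 and SAP 4.2.1 define recurrence by examination: a palpable defect or bulge within 7 cm of the repair. Neither sets a condition on cause. Protocol 14.5 expresses the 2-year version as "the proportion of subjects with any recurrences of hernia on the same anatomical region as the target lesion through 2 years post-procedure".

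**Other capture provisions.** Table 7 of the protocol has a separate recurrence row, marked at 30 days, 3 months and years 1-2, with no relatedness condition. SAP 7.10 says: "AEs for all subjects will be collected from consent through the study exit".

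**Who is counted.** SAP 7.9.3.5: "The analysis set for the secondary objectives will be the FAS with available data". Protocol 14.11 excludes imputation for secondary endpoints, and SAP 7.2 summarises categorical data as frequencies and percentages. The detailed availability rules in SAP 7.4 are written for 30-day assessments only.

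**The concern.** There are two gaps.

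First, an endpoint that does not depend on cause is derived from a form whose content, after day 30, does. A surgeon who confirms a bulge at the repair but puts it down to weight gain or straining could classify it as unrelated and, on the wording of 12.1, not report it as an AE. Under version 5.0 the CEC adjudicates only through 30 days, so no committee would review that call. Any error runs one way, towards a lower recurrence rate.

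Second, nothing says whether a subject with no recurrence on record and no year-2 contact is a non-event or is left out. Years 1 and 2 are planned as telephone visits, and protocol 10.10.6 lets subjects disengage, after which data collection requirements lapse, so some missing 2-year status is foreseeable. The choice of denominator moves the rate, and as written it could be made after the data are seen.

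This is the only long-term secondary endpoint, read against benchmarks of 15% (inguinal) and 37% (ventral).

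**Working it through.** **The plan's own figures.** The documents give no sample size, precision or attrition figure for 2-year recurrence. The cohort sizes behind it reproduce: 86/0.9 = 95.6, so 96 per cohort; 172/0.9 = 191.1, so 192 in total. Exact binomial power is 86.1% for safety (n = 86, reject at 16 or fewer events) and 90.4% for effectiveness (n = 172, reject at 156 or more successes), matching the stated 86% and 90%. None of this is in dispute.

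**Inputs.** Literature 2-year recurrence from protocol Table 16: 0.6% inguinal, 10.9% ventral. Loss over 2 years is an assumption. The 10% in the documents is the allowance for the primary endpoints, so I use 10% and 20%, with 30% as an outer case.

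**Denominator effect.** Let R be the true 2-year risk and d the 2-year loss, with constant hazards and loss unrelated to recurrence. Put L = -ln(1-R) and M = -ln(1-d).

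- Recurrence seen before loss: E = L/(L+M) × [1 - (1-R)(1-d)]
- Completed without recurrence: C = (1-R)(1-d)
- All treated in the denominator: E
- Events plus completers: E/(E+C)
- Only subjects with status known at 2 years: R(1-d)/(1-d) = R

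Ventral, d = 0.10: E = 0.11541/0.22077 × (1 - 0.8019) = 0.5228 × 0.1981 = 0.1036; E/(E+C) = 0.1036/0.9055 = 0.1144.

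Ventral, d = 0.20: E = 0.11541/0.33855 × (1 - 0.7128) = 0.3409 × 0.2872 = 0.0979; E/(E+C) = 0.0979/0.8107 = 0.1208.

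| True 2-year rate | Assumed loss | All treated | Events plus completers | Known 2-year status |
|---|---|---|---|---|
| Ventral 10.9% | 10% | 10.4% | 11.4% | 10.9% |
| Ventral 10.9% | 20% | 9.8% | 12.1% | 10.9% |
| Ventral 10.9% | 30% | 9.2% | 12.9% | 10.9% |
| Inguinal 0.6% | 10% | 0.57% | 0.63% | 0.6% |
| Inguinal 0.6% | 20% | 0.54% | 0.67% | 0.6% |

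For scale, the approximate 95% half-width at 10.9% is 1.96 × √(0.109 × 0.891/96) = 6.2 points with 96 subjects and 6.6 points with 86.

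**Attribution filter.** If a share m of recurrences stays off the form, the rate reads R(1-m). The documents give no basis for m. As pure illustration, ventral 10.9% (96 × 0.109 = 10.5 expected recurrences) would read 9.8% at m = 10% (9.4 recurrences), 8.2% at 25% (7.8) and about 5.5% at 50% (5.2). Nothing suggests the upper values are likely.

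**The case against.** The strongest reply is that the plan solicits recurrence well outside the AE filter. Besides the Table 7 row, protocol 10.1.6 requires an in-person visit when a subject reports a recurrence, and unconfirmed reports are tabulated separately. Protocol 5.2.2 sends even secondary hernias more than 7 cm away to an AE eCRF without an attribution test, so it would be odd if recurrences at the repair were captured less fully. The related category is also wide: for analysis it "will include Possible, Probably, and Causal", and a weak link that cannot be excluded counts as possible even where other causes exist. A bulge at the repair would usually qualify.

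Much of this stands. A reader might infer that recurrences will in fact be lost. The documents do not support that: they contain a conflict, and the case report form that might settle it is not among them. What remains is that the SAP names the AE CRF rather than the Table 7 item as its source, and that Table 8 allows an event attributable to another cause to be classed as not related.

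A reader might also infer that loss to follow-up necessarily biases the rate. It need not. The planned set is subjects with available data, not all treated, and a known-status proportion is unbiased if loss is unrelated to recurrence. But the SAP does not say that this is what available means at 2 years.

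Finally, the secondary endpoints are descriptive, their goals are benchmarks only, and protocol 14.5 already foresees two-sided 95% intervals where appropriate. That limits the stakes and leaves the gap in place.

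**Conclusion.** The point holds as an inconsistency to reconcile plus an undefined denominator. It is not a demonstrated loss of events or an established bias.

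The filter can only lower the rate. Its size is unknown and probably small. The denominator effect, under 10-20% non-informative loss with constant hazards, is about 0.5 to 1.2 points on a ventral rate of 10.9%, in a direction set by a rule that the SAP does not give. That is well inside the sampling error of one cohort. If loss is related to recurrence, these figures do not apply and the direction cannot be stated.

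A reader might go on to infer that the comparison with the benchmarks is at risk. At the literature rates it is not: 0.6% against 15% and 10.9% against 37% leave margins far wider than these shifts. Study success does not depend on this endpoint. The reason to act is that the only long-term secondary result should have one source and one denominator, fixed before the 2-year data are seen.

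**What to change.** In SAP 7.9.3.1, count every investigator-confirmed recurrence through 2 years regardless of attribution, and name as source the Table 7 recurrence item together with the AE CRF. Reconcile protocol 12.1 and 12.4 with this, so that confirmed recurrences are recorded whatever their relatedness.

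In SAP 7.4 or 7.9.3.5, define who has available data at 2 years, including subjects with an earlier recurrence who then leave and subjects whose last contact precedes the year-2 window.

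Report a Kaplan-Meier or interval-censored 2-year estimate by cohort with a 95% CI, censoring at last contact with known recurrence status. It must accommodate the visit window of 730 ± 30 days, that is days 700 to 760. A cut at exactly day 730 would drop recurrences dated on days 731 to 760 and censor subjects seen earlier in the window.

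Cost: a few sentences in the SAP, slightly more analysis work, and no new visits or assessments. The protocol wording can wait for the next revision, but it then needs FDA and IRB approval under protocol 16.6.

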7.9.3.2 Hypotheses

The secondary objectives are not powered in this study. Instead, the secondary endpoints will be analyzed using descriptive statistics, which broadly negate the need for multiplicity adjustments.

7.9.3.3 Performance Requirements

The role of the secondary endpoints is to explore additional effects and outcomes associated with either the procedure or the disease state. The pre-specified performance goals (also referred as performance targets for the secondary objectives) serve as benchmarks for interpretation rather than thresholds for statistical significance of clinical trial success in this study.

Performance targets for each of the secondary objectives can be found in the CIP.

7.9.3.4 Analysis Methods

Descriptive statistics will be provided as defined in section 7.2.

7.9.3.5 Determination of Subjects/Data for Analysis

The analysis set for the secondary objectives will be the FAS with available data. Data availability for assessments through 30 days will follow the logic described in section 7.4. The secondary endpoints will be analyzed for the inguinal and ventral hernia cohorts separately and when combined.

7.9.4 Ancillary Objectives

Descriptive analyses of ancillary objectives will be exploratory in nature and are not intended as a focus of the study for the evaluation of the study device.

Endpoint	Endpoint Definition and Derivation
Estimated intraoperative blood loss	Estimated blood loss is assessed by the study site on the Procedure CRF.
Transfusion rate through 30 days	Use of transfusion was assessed by the study site on the AE CRF.
Mortality through 30 days	Death is assessed by the study site on the AE and Exit CRFs.
Device- and/or procedure-related AEs through 2 years	The CEC assessment of device and/or procedure related will be used as the primary source of relatedness. For events without CEC adjudication, the study site assessment will be used from the AE CRF.
Hospital length of stay	Hospital length of stay is determined from the start of the procedure (first incision) and discharge time/date assessed by the study site on the Procedure CRF.
Readmission rate through 2 years post procedure	Admission for a direct consequence or complication associated with the treated hernia or with the surgical procedure to treat the hernia. A readmission is determined by the study site on the AE CRF.

Reoperation rate through 2 years post procedure	Operation for a direct consequence or complication associated with the treated hernia or with the surgical procedure to treat the hernia. A reoperation is determined by the study site on the AE CRF.
Surgeon experience	Surgeon experience is recorded by each surgeon after their 1 st procedure and after their 10 th /last procedure. These are recorded on the Surgeon_ex CRF and will be assessed by visit.
Pain scores at baseline, 30-days, and 3-months (Abdominal Core Health Quality Collaborative [ACHQC] questionnaire)	Pain scores were assessed by study subjects on the ACHQC questionnaire at baseline, 30-days, and 3-months. Summaries of the data will include worst and average pain in the last 7 days as well as current pain at the time of the assessment.

The analysis set for these ancillary objectives will be the FAS with available data. Data availability for assessments through 30 days will follow the logic described in section 7.4. The ancillary endpoints will be analyzed for the inguinal and ventral hernia cohort respectively.

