Study Procedures and Assessments	
Screening, Surgical Procedure, Hospital Discharge, and Post-Discharge Follow-Up at 30 days (<math>\pm 7</math> days), 3 months (<math>\pm 14</math> days), 1 year (<math>\pm 30</math> days) and 2 years (<math>\pm 30</math> days):
 
Screening: To determine study eligibility and collect baseline information (i.e., demographics, medications, medical history, surgical history)
 
Surgical Procedure: To re-confirm eligibility criteria, procedure set-up and take-down, medication changes, interoperative complication evaluation, disease state evaluation, procedure success, conversion, adverse event evaluation, device deficiency evaluation
 
Up to Hospital Discharge: Adverse event evaluation, subject complication rate, disease state evaluation, protocol deviation and medications.
 
Post-Discharge Follow-Up: Adverse event evaluation, subject complication rate, disease state evaluation, length of hospital stay, readmission (if applicable), reoperation (if applicable), recurrence (if applicable), chronic pain, protocol deviation, medications, and study exit.

Safety Assessments	
Data on the presence of adverse events (AEs) will be collected from the time of consent. Safety assessments will be based on the full analysis set (FAS). Data including AE term, incidence, severity, and procedure/device relatedness will be reported. AEs for all FAS subjects will be collected from time of consent through the study exit.
 
AEs will be assessed by the Investigator and the sponsor. All Serious Adverse Events (SAE), deaths, and Surgical Site Events (SSEs) will be adjudicated by an external, independent Clinical Events Committee (CEC).
 
AEs occurring in subjects excluded from the full analysis set will be followed post-consent through study exit and will be reported in a listing in the clinical study report (CSR). These AEs will not be included in the FAS summary for either AE reporting or the analysis of the primary and secondary endpoints.
 
AEs and Device Deficiencies will be summarized in tables displaying the

*Medtronic Business Restricted*

	number of events, and the number and percentage of subjects with events.

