## 18.10 ACHQC Questionnaire

### Abdominal Core Health Quality Collaborative

What would your doctor need to know regarding your experience of your hernia (or hernia surgery) to take good care of you?

*Please respond to each item by marking one box per row*

How intense was your pain at its worst?	 Had no pain  Mild  Moderate  Severe  Very Severe
How intense was your average pain?	 Had no pain  Mild  Moderate  Severe  Very Severe
What is your level of pain right now?	 Had no pain  Mild  Moderate  Severe  Very Severe
For the following statements, please circle the number that is most appropriate for you	
1. My abdominal wall has a huge impact on my health	1. Strongly Disagree 2. Moderately disagree 3. Slightly disagree 4. Slightly agree 5. Moderately agree 6. Strongly agree

*Medtronic Business Restricted*

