# Enable Hernia Repair Clinical Investigation Plan

MDT21022

Version 5.0

Page 107 of 116

Medtronic

2. My abdominal wall causes me physical pain	

1. Strongly Disagree

2. Moderately disagree

3. Slightly disagree

4. Slightly agree

5. Moderately agree

6. Strongly agree

3. My abdominal wall interferes when I perform strenuous activities (e.g. heavy lifting)	

1. Strongly Disagree

2. Moderately disagree

3. Slightly disagree

4. Slightly agree

5. Moderately agree

6. Strongly agree

4. My abdominal wall interferes when I perform moderate activities (e.g. bowling, bending over)	

1. Strongly Disagree

2. Moderately disagree

3. Slightly disagree

4. Slightly agree

5. Moderately agree

6. Strongly agree

5. My abdominal wall interferes when I walk or climb stairs	

1. Strongly Disagree

2. Moderately disagree

3. Slightly disagree

4. Slightly agree

5. Moderately agree

6. Strongly agree

*Medtronic Business Restricted*

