7.2 General Methodology

All data analyses will be performed by Medtronic or its designee. All statistical analyses will be performed using the Statistical Analysis System (SAS, version 9.4 or higher, SAS Institute Inc. Cary, NC) or other widely accepted statistical or graphical software.

Descriptive statistics will be used to summarize study outcomes. Continuous variables will be summarized using number of subjects (n), mean, standard deviation, median, 25th quartile, 75th quartile, minimum, and maximum. Categorical variables will be summarized using frequencies and percentages.

The study safety and performance analyses related to the procedure and to data through 30 days will occur after all subjects complete the 30-day follow-up visit, discontinued prior to the visit, or were confirmed to miss the visit. A CSR will be prepared once all data collection has ended and all subjects have completed the 30-day follow-up or have exited. A final report will be completed at the end of the 2-year follow-up.

For consideration of study visits, the target number of days from the procedure to each visit is 90 days, 365 days, and 730 days for the 3-month, 1-year, and 2-year visits, respectively.

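### Chronic pain is listed as a follow-up assessment but has no definition or analysis, and the planned pain-score summaries make no within-subject comparison with baseline, so they can mask new or worse pain.

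*SAP*

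**What the plan says.** In the protocol synopsis (Section 3), the row on study procedures and assessments gives the post-discharge items as including "reoperation (if applicable), recurrence (if applicable), chronic pain, protocol deviation, medications, and study exit". Neither document attaches an item, threshold, time point or derivation to chronic pain. It is not in the ancillary lists of Protocol 5.3 and 14.6 or SAP 4.3, and it has no row in Protocol Table 7.

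The one patient-reported pain endpoint is ancillary. SAP 7.9.4 states: "Pain scores were assessed by study subjects on the ACHQC questionnaire at baseline, 30-days, and 3-months". It continues: "Summaries of the data will include worst and average pain in the last 7 days as well as current pain". The default method in SAP 7.2 is: "Categorical variables will be summarized using frequencies and percentages".

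Protocol Table 7 schedules the ACHQC questionnaire at screening, 30 days and 3 months. Appendix 18.10 shows three pain items with five ordered answers from no pain to very severe, the first being "How intense was your pain at its worst". Twelve abdominal-wall statements follow, including "My abdominal wall causes me physical pain". SAP 7.9.4 does not mention these twelve.

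On status, SAP 7.9.4 says: "Descriptive analyses of ancillary objectives will be exploratory in nature and are not intended as a focus of the study".

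**The concern.** The questionnaire is scheduled before and after surgery in the same subjects, so each subject can serve as their own control. The plan does not say that this pairing will be used. If some candidates have pain before repair and lose it afterwards, the share with pain falls, and that fall can absorb subjects who had little pain before and have more afterwards. A reader of the report would see a favourable trend and could not tell how many subjects got worse. If different subjects answer at each time point, differences in who responded are also mixed into the apparent change.

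What is at stake is the readability of one descriptive result, and whether an assessment named in the synopsis has an identifiable result.

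**Working it through.** The documents give no pain rate, sample size or power for pain, so there is no figure of the plan's own to reproduce. The check asks what two separate summaries can reveal.

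**Inputs.** n = 86 per cohort, the evaluable size for primary safety in SAP Section 6. It is borrowed for scale and is not a forecast of paired 3-month questionnaires. All pain rates below are assumptions.

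**Notation.** B = subjects with moderate-or-worse pain at baseline, F = the same at 3 months, R = those in B whose pain resolves, W = those outside B with new moderate-or-worse pain. Then F = B − R + W.

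**What the two summaries allow.** They fix B and F, but not R and W. The possible range is max(0, F − B) ≤ W ≤ min(F, n − B). With B = 43 (50.0%) and F = 13 (15.1%), the lower limit is max(0, −30) = 0 and the upper limit is min(13, 43) = 13. So W lies between 0 and 13, or 0% and 15.1%.

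**Two cohorts with identical summaries.**

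| | Baseline | Resolved | New | 3 months |
|---|---|---|---|---|
| A | 43 | 30 | 0 | 43 − 30 + 0 = 13 |
| B | 43 | 39 | 9 | 43 − 39 + 9 = 13 |

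Cohort A has no new pain; cohort B has 9/86 = 10.5%. A shift table separates them at once.

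**In proportions.** With b the baseline share, r the share of those improving and w the new-onset share among the rest, follow-up prevalence is b(1 − r) + (1 − b)w and the new-pain share is (1 − b)w.

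- b = 0.50, r = 0.80, w = 0.20: 0.10 + 0.10 = 20% at follow-up, of which 10% is new.
- b = 0.40, r = 0.75, w = 0.15: 0.10 + 0.09 = 19%, of which 9% is new.
- b = 0.60, r = 0.80, w = 0.30: 0.12 + 0.12 = 24%, of which 12% is new.

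**Range.** At n = 86, with b of 30%, 50% or 70%, r of 70% or 90%, and w of 0%, 10% or 20%, prevalence falls in every combination while the new-pain share runs from 0% to 14.0% (12/86).

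**Is the paired result informative at this size?** The Clopper-Pearson 95% interval for 9/86 is 4.9% to 18.9%; for 0/86 the upper limit is 4.2%. The two illustrative cohorts would be reported distinguishably.

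**The case against.** The strongest reply is that pain scores are not the only route by which pain is reported. Protocol 12.1 treats a pre-existing condition as an adverse event if its nature or severity worsens, which is itself a comparison with the subject's own earlier state. Protocol 10.4 provides for pain beyond normal limits to be reported as an adverse event of Clavien-Dindo Grade I or higher. Under Protocol 12.5.2 and Table 11, incisional pain is exempt only for 72 hours unless it worsens. Related events of Grade I or higher through 30 days enter a secondary endpoint (SAP 7.9.3.1), related adverse events through 2 years are an ancillary endpoint (SAP 7.9.4), and adverse events are tabulated by preferred term and relatedness (SAP 7.10). Relatedness is broad: Protocol Table 8 counts possible as related.

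Most of this stands. A reader might infer that new pain will be hidden or never reported; the documents do not support that. The route narrows the gap without closing it. It depends on the investigator reporting an event, and nothing ties a questionnaire answer to such a report. After 30 days only events the surgeon deems attributable are reported (Protocol 12.1). It yields no patient-reported rate of worsening.

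Three further replies also stand. The synopsis places chronic pain under study procedures and assessments, not in its safety-assessments row, so reading it as a promised safety endpoint goes too far. That the pain summaries are by visit is inferred from the listed time points; SAP 7.9.4 uses that phrase only for surgeon experience, and its wording for pain does not exclude a change from baseline. Finally, the documents do not say how common pre-operative pain is in these subjects.

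**Conclusion.** The point holds as a low-cost improvement to an ancillary analysis. Chronic pain is named once and never defined or analysed. The patient-reported pain data are planned as summaries without a specified within-subject comparison, and such summaries cannot identify new or worse pain. In the illustration, a fall from 50.0% to 15.1% fits any new-pain share from 0% to 15.1%.

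That size rests wholly on assumed pain rates and a borrowed n of 86; the actual extent of masking cannot be known from the documents. It also rests on the inference that the summaries are separate at each time point. Means in place of percentages would have the same limit.

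A reader might go further and infer that the safety conclusion is at risk. It is not: the endpoint is exploratory, has no performance goal, and no primary or secondary conclusion depends on it.

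**What to change.** In SAP 7.9.4, for each of the three pain items and by hernia cohort, add a baseline-by-visit shift table at 30 days and at 3 months in subjects with both assessments. Report:

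- the number of paired observations;
- the proportion in a worse category than at baseline;
- the proportion moving from none or mild to moderate or worse;
- a Clopper-Pearson 95% interval for each proportion.

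Label all of it descriptive. The moderate-or-worse cut is a reporting choice, since the documents give none.

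Then reconcile the synopsis term with the analysis: state which item, category and visit represent chronic pain, or remove the term.

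The cost is a few SAP sentences and one extra table per cohort from data already scheduled for collection, with no new visit, subject, hypothesis test or multiplicity change. There are two downsides. The pain result may look less favourable. A one-category shift on a five-level item may be measurement noise, so the none-or-mild to moderate-or-worse proportion should be read beside it.
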